#### 5.8.1.5.3 Additional recommendations for patients in AZD6244 arm

- Ophthalmologic exam (including slit-lamp) – to be performed in patients experiencing visual disturbances while in the trial.

- Echocardiogram or MUGA scan (measurement of LVEF) – to be performed in patients with symptoms (AEs) suggestive of cardiac impairment (congestive heart failure, oedema, dyspnea).
- Decreases in LVEF from baseline (if known) may be investigated according to the algorithm (note- this appears as a word doc in the in AZD6244 ISS study guide)
- All new dyspnea AEs or worsening of pre-existing dyspnea AEs should be followed according to the dyspnea algorithm (note this appears in the AZD6244 ISS study guide)

## **5.9 Protocol Evaluation**

5.9.1 Prior to each treatment cycle (please refer to Section **5.3** for definition of a cycle):

5.9.1.1 SOAP progress note.

5.9.1.2 Laboratory examination:

5.9.1.2.1 Hematological Profile: CBC with differential and platelet count.

5.9.1.2.2 Biochemical Profile: Sodium, potassium, chloride, CO2, BUN, creatinine, glucose, AST, ALT, alkaline phosphatase, bilirubin, albumin, total protein, LDH, calcium, phosphorous and magnesium.

5.9.1.3 Vital signs including weight.

5.9.2 Restaging and Imaging:

Restaging will be performed at the end of every two cycles, +/- 1 week, as defined for each treatment arm. Therefore, restaging will be performed every 6 weeks +/- 1 week for the Erlotinib, AZD6244, and Lapatinib arms; every 8 weeks +/- 1 week for the MK-2206 arm, and every 12 weeks +/- 1 week for the Sunitinib arm. Imaging modalities will consist of CT or MRI, as appropriate for disease evaluation. The use of FDG-PET will be allowed but it would be considered exploratory and its results will not be used for treatment decisions.

## **5.10 Duration of therapy / off treatment criteria**

In the absence of treatment delays due to adverse events, treatment under any of the investigational arms (Erlotinib, AZD6244, MK2206, Lapatinib and Sunitinib) may continue until one of the following criteria applies:

- Disease progression as defined by Section **13**.
- Intercurrent illness that prevents further administration of treatment.
- Delay of treatment due to toxicity of  $\geq 3$  weeks.
- Unacceptable adverse event(s)\*.
- Non-compliance to therapy regimen.
- Pregnancy
- Patient decides to withdraw from the study arm or stop therapy.

- Deterioration of the patient's condition that render further treatment unacceptable in the judgment of the investigator.

\* Patients removed from study arm due to unacceptable adverse events, will continue to be followed in clinic, at least every 4 weeks until all adverse events have resolve to grade I or less.

### **5.11 Duration of follow up**

All patients that are not receiving active investigational treatment (Erlotinib, AZD6244, MK2206, Lapatinib and Sunitinib), including those on the NOS arm and those deemed as "Screen Failures," will continue to be followed until death or the patient decides to withdraw from the study. These patients will be followed either with clinic visits or phone interviews every 4 months (+/- 2 months). If patient is receiving treatment at an outside facility, pertinent medical records should be sent to the PI at the participating institution for data collection. The following information will be collected:

- Date of follow up
- Is patient dead or alive?
- If dead, document exact date of death.
- Further chemotherapy / biotherapy treatment(s)
  - Drug name(s)
  - Date(s) of administration (month/year)
  - Response to treatment
- Document date of disease progression
- Document ECOG PS

\* No toxicity information will be collected for patients being followed in the NOS arm.

### **5.12 Off Study Criteria**

Patients will be removed from study for:

- Screening failure
- Death
- Patient decides to withdraw from the study
- At the investigator's discretion
- Lost to follow-up

The reason for study removal and the date the patient was removed will be documented in the Case Report Form.

### **5.13 Off-Study Procedure**

Authorized staff must notify Central Registration Office (CRO) when a subject is taken off-study. A Participant Status Updates Form from the web site (<http://home.ccr.cancer.gov/intra/eligibility/welcome.htm>) main page must be completed and

sent via encrypted email to: NCI Central Registration Office (HOIS) [[contact]](mailto:[contact]).

## **6 DOSING DELAYS/DOSE MODIFICATIONS**

Patients enrolled in one of the experimental study arms may continue to receive additional cycles of therapy provided that the patient meets the following criteria on Day 1 of each cycle:

- ANC > 1,000/mcL
- Platelets > 100,000/mcL
- Non-hematologic toxicity recovered to < grade 2 (or tolerable grade 2 or baseline)
- No evidence of progressive disease

In the event of an adverse event at least possibly related to the agent, the doses of such agent should be adjusted according to the guidelines shown in the Dose Delays / Dose Modifications tables shown below (Sections 6.1 and 6.2). If an adverse event is not covered in such tables, doses may be reduced or held at the discretion of the investigator for the subject's safety.

Subjects with adverse events that are manageable with supportive therapy may not require dose reductions (e.g., nausea/vomiting ~~may~~ be treated with antiemetics, diarrhea may be treated with loperamide, and electrolyte ~~abnormalities~~ may be corrected with supplements rather than by dose reduction).

Subjects will be withdrawn from the study arm if they fail to recover to CTC Grade 0-1 or tolerable grade 2 (or within 1 grade of starting values for pre-existing laboratory abnormalities) from a treatment-related adverse event within 21 days OR they experience agent related adverse events requiring dose modification despite two previous dose reductions (i.e. would require a 3rd dose reduction) unless the investigator and CTEP monitor agree that the subject should remain in the study arm because of evidence that the patient is/may continue deriving benefit from continuing study treatment (i.e. patient has PR, CR, SD > 3 months). The appropriate reduced dose will be determined after discussion between the principal investigator and CTEP monitor.

### **6.1 CTEP agents**

#### **6.1.1 Erlotinib**

**Table 6. Erlotinib Monotherapy Dose Level Reductions**

Dose Level	Erlotinib Dose
Starting Dose	150 mg/day
First Dose Reduction	100 mg/day
Second Dose Reduction	75 mg/day

**Table 7.** Dosage Modification Criteria for **Erlotinib**–related Toxicities

Toxicity	Grade	Erlotinib dosage modification*	Guideline for management
Keratitis	1	None	No intervention
	2 (if < 14 days)	None	Preservative-free artificial tears, ointments, and/or other therapies as clinically indicated, with a follow-up examination within 2 weeks
	2 (if > 14 days)	Hold until recovery to $\leq$ grade 1 And then Reduce 1 dose level	
	$\geq 3$	Hold until recovery to $\leq$ grade 1 And then Reduce 1 dose level*	
Diarrhea	1	None	No intervention
	2	None if tolerable If not tolerable, hold until resolution to grade $\leq 1$ , then resume at the same dose. If intolerable grade 2 recurs after resumption, hold until resolution to grade $\leq 1$ and resume with 1 dose reduction.	Loperamide (4 mg at first onset, followed by 2 mg every 2–4 hrs until diarrhea free for 12 hrs)
	$\geq 3$ (despite optimal loperamide use)	Hold until recovery to $\leq$ grade 1 And then Reduce 1 dose level*	
Rash	1	None	No intervention
	2	None if tolerable If not tolerable, hold until resolution to grade $\leq 1$ , then resume at the same dose. If intolerable grade 2 recurs after resumption, hold until resolution to grade $\leq 1$ and resume with 1 dose reduction.	Any of the following: minocycline, topical tetracycline or clindamycin, topical silver sulfadiazine, diphenhydramine, oral prednisone (short course)
	$\geq 3$	Hold until recovery to $\leq$ grade 1 And then Reduce 1 dose level	

Bilirubin	$\geq 3 \times \text{ULN}$	Hold until grade $\leq 2$ And then Reduce 1 dose level	
Liver transaminase	$> 5 \times \text{ULN}$	Hold until grade $\leq 2$ And then Reduce 1 dose level	
Signs and symptoms of interstitial pneumonitis		Hold pending diagnosis Permanently discontinue if diagnosis is confirmed and considered possibly related to erlotinib	Patient should be thoroughly evaluated, closely monitored, and supported as clinically indicated
Other toxicity	$\geq 2$ prolonged clinically significant toxicity	Hold until recovery to $\leq$ grade 1 And then Reduce 1 dose level*	Treatment as appropriate

\*if dose has been previously held for grade 2 rash or diarrhea, and grade 2 symptoms recur, OR if the patient finds the symptoms unacceptable, hold dose until recovery to  $\leq$  grade 1 and then reduce dose one level

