## **5.7 Agent Administration**

Treatment will be administered on an outpatient basis. Reported adverse events and potential risks from the agents used in this protocol are described in Section [7](#). Appropriate dose modifications for these agents are described in Section [6](#). No investigational or commercial agents or therapies other than those described below may be administered with the intent to treat the patient's malignancy.

Patients in all treatment arms (Erlotinib, AZD6244, [MK2206](#), Lapatinib and Sunitinib) will be provided with a Medication Diary ([Appendix B](#)). They will be instructed in its use and asked to bring the diary with them to each appointment. A new copy of the Medication Diary will be given to patients whose dose is reduced due to adverse events. Patients should log in their daily dose onto the diary, including missed, skipped, or vomited doses. If the patient vomits after taking the tablets, the dose is replaced only if the tablets can actually be seen and counted. If a patient misses a dose, he or she should be instructed to resume dosing with the next scheduled dose.

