#### **7.1.1 CAEPRs for CTEP-Supplied Investigational Agent(s)**

##### **7.1.1.1 Erlotinib (OSI-774, NSC 718781)**

**Comprehensive Adverse Events and Potential Risks list (CAEPR)**  
**for**  
**Erlotinib (Tarceva® , NSC 718781)**

The Comprehensive Adverse Events and Potential Risks list (CAEPR) provides a single list of reported and/or potential adverse events (AE) associated with an agent using a uniform presentation of events by body system. In addition to the comprehensive list, a subset, the Specific Protocol Exceptions to Expedited Reporting (SPEER), appears in a separate column and is identified with bold and italicized

text. This subset of AEs (SPEER) is a list of events that are protocol specific exceptions to expedited reporting to NCI (except as noted below). Refer to the 'CTEP, NCI Guidelines: Adverse Event Reporting Requirements' [http://ctep.cancer.gov/protocolDevelopment/electronic\\_applications/docs/aeguidelines.pdf](http://ctep.cancer.gov/protocolDevelopment/electronic_applications/docs/aeguidelines.pdf) for further clarification. Frequency is provided based on 3622 patients. Below is the CAEPR for erlotinib (Tarceva®).

**NOTE:** Report AEs on the SPEER **ONLY IF** they exceed the grade noted in parentheses next to the AE in the SPEER. If this CAEPR is part of a combination protocol using multiple investigational agents and has an AE listed on different SPEERs, use the lower of the grades to determine if expedited reporting is required.

Version 2.5, March 25,  
2015

Adverse Events with Possible Relationship to Erlotinib (Tarceva®) (CTCAE 4.0 Term) [n= 3622]			Specific Protocol Exceptions to Expedited Reporting (SPEER)
Likely (>20%)	Less Likely (<=20%)	Rare but Serious (<3%)	
BLOOD AND LYMPHATIC SYSTEM DISORDERS			
		Disseminated intravascular coagulation 	
		Hemolytic uremic syndrome 	
		Thrombotic thrombocytopenic purpura 	
CARDIAC DISORDERS			
		Myocardial infarction 	
EYE DISORDERS			
	Conjunctivitis		Conjunctivitis (Gr 2)
	Dry eye		Dry eye (Gr 2)
		Eye disorders - Other (corneal perforation)	
	Eye disorders - Other (eyelash ingrowth and/or thickening)		
		Keratitis	
GASTROINTESTINAL DISORDERS			
	Abdominal pain		Abdominal pain (Gr 3)
Diarrhea			Diarrhea (Gr 3)
	Dry mouth		Dry mouth (Gr 2)
	Dyspepsia		Dyspepsia (Gr 2)
	Gastrointestinal hemorrhage 		

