## *Safety profile*

### *Adverse Events Associated with OSI-774*

A comprehensive list of AEs possibly related to OSI-779 is provided in the CAEPR. Additional information can also be found in the Investigator's Brochure and the Package Insert. A few common or serious AEs are described below.

Rash or dermatosis: (Grades 1-3) has been reported in many subjects (~50%) during the first several days of treatment, although severity diminishes after 4 weeks of therapy. The use of topical agents (i.e., diphenhydramine, corticosteroids) and oral antibiotics (tetracycline) has been instituted in some patients with variable results. In patients with severe rash, treatment has been discontinued or the study drug dose reduced. The etiology of the rash is still unknown, but may be related to the mechanism of action of OSI-774.

Nausea and diarrhea: (Grades 1-2) have been observed in approximate half of all subjects treated with OSI-774. Both adverse events are transient and usually do not require a reduction in dosage. Diarrhea is well controlled in most patients by either the use of loperamide or dose reduction. All ongoing clinical trials recommend the institution of therapy with loperamide. As of June 2001, no significant drug interactions have been observed between OSI-774 and loperamide.

Hepatic toxicities: Cases of hepatic failure and hepatorenal syndrome (including fatalities) have been reported during use of OSI-779, particularly in patients with baseline hepatic impairment. Therefore, periodic liver function testing (transaminases, bilirubin, and alkaline phosphatase) is recommended. In the setting of worsening liver function tests, dose interruption and/or dose reduction with frequent liver function test monitoring should be considered. OSI-779 dosing should be interrupted or discontinued if total bilirubin is  $>3$  x ULN and/or transaminases are  $>5$  x ULN in the setting of normal pretreatment values.

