Renal insufficiencies: Cases of hepatorenal syndrome, acute renal failure (including fatalities), and renal insufficiency have been reported. Some were secondary to baseline hepatic impairment while others were associated with severe dehydration due to diarrhea, vomiting, and/or anorexia, or concurrent chemotherapy use. In the event of dehydration, particularly in patients with contributing risk factors for renal failure (e.g., pre-existing renal disease, medical conditions or medications that may lead to renal disease, or other predisposing conditions including advanced age), OSI-779 therapy should be interrupted and appropriate measures should be taken to intensively rehydrate the patient. Periodic monitoring of renal function and serum electrolytes is recommended in patients at risk of dehydration.

**Gastrointestinal perforation:** Patients receiving OSI-779 are at increased risk of developing gastrointestinal perforation, which was observed uncommonly. Some cases had a fatal outcome. Patients receiving concomitant anti-angiogenic agents, corticosteroids, NSAIDs, and/or taxane-based chemotherapy, or who have prior history of peptic ulceration or diverticular disease, are at increased risk. OSI-779 should be permanently discontinued in patients who develop gastrointestinal perforation.

**Bullous and exfoliative skin disorders:** Bullous, blistering, and exfoliative skin conditions have been reported, including very rare cases suggestive of Stevens-Johnson syndrome/toxic epidermal necrolysis (which in some cases were fatal). OSI-779 treatment should be interrupted or discontinued if the patient develops severe bullous, blistering, or exfoliating conditions.

**Ocular disorders:** Very rare cases of corneal perforation or ulceration have been reported during use of OSI-779. Other ocular disorders, including abnormal eyelash growth, keratoconjunctivitis sicca or keratitis have been observed with OSI-779 treatment and are known risk factors for corneal perforation/ulceration.

OSI-779 therapy should be interrupted or discontinued if patients present with acute/worsening ocular disorders such as eye pain.

**Fertility and teratology:** These studies have not been conducted with OSI-774, and safety for women of childbearing capacity cannot be implied from the existing data. OSI-774 has not been tested for carcinogenic activity in a lifetime rodent bioassay.

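### Table 7 permits but does not require an erlotinib hold for acute or worsening eye symptoms with keratitis below grade 3, where the protocol's own safety text says to interrupt or stop

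*Combined protocol and SAP*

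**What the plan says.** Section 5.7 sends the reader to Section 6 for dosing changes: "Appropriate dose modifications for these agents are described in Section" 6. Section 6 directs that doses for related adverse events follow its tables, and leaves events that the tables do not cover to the investigator's discretion.

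Table 7 (Section 6.1.1) has four keratitis rows:

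- Grade 1: no dose change and no intervention.
- Grade 2 for under 14 days: no dose change; management is "Preservative-free artificial tears, ointments, and/or other therapies as clinically indicated, with a follow-up examination within 2 weeks".
- Grade 2 for more than 14 days: hold until grade 1 or lower, then reduce one level.
- Grade 3 or higher: the same hold and reduction.

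The table's footnote, whose asterisk also stands on the dosage column header, adds a tolerability trigger: "OR if the patient finds the symptoms unacceptable, hold dose until recovery to" grade 1 or lower.

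The erlotinib safety text in Appendix A (18.1.1.3, ocular disorders) says that "keratoconjunctivitis sicca or keratitis have been observed with OSI-779 treatment and are known risk factors for corneal perforation/ulceration" and that "OSI-779 therapy should be interrupted or discontinued if patients present with acute/worsening ocular disorders such as eye pain". It prints the code OSI-779, but it stands in the erlotinib section under a heading for OSI-774, so erlotinib is plainly meant. The erlotinib adverse event list in Section 7.1.1.1 puts both keratitis and "Eye disorders - Other (corneal perforation)" in the rare but serious column (under 3%).

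**The concern.** Table 7 sorts keratitis by grade and duration. The safety text acts on how the patient presents: acute onset or worsening. A patient whose keratitis is worsening or painful, but is still grade 1 or early grade 2, meets the second test and not the first. A site that follows the table exactly makes no dose change, and for grade 2 may wait up to two weeks before looking at the eye again.

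The stake is patient safety, because the protocol itself links keratitis to corneal perforation and ulceration. Nothing statistical is at stake: the response endpoint, the two-stage stopping rules, the sample size and the analysis do not depend on this row.

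**Working it through.** There is no plan figure to reproduce. The check sets the texts side by side.

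**1. What each text requires**

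| Situation | Section 6 and Table 7 | Appendix A safety text |
|---|---|---|
| Grade 3 or higher | Hold, then reduce | Interrupt or stop if acute or worsening; no conflict |
| Grade 2, more than 14 days | Hold, then reduce | As above; no conflict |
| Grade 2, exactly day 14 | No row applies | As above |
| Grade 2, under 14 days, acute or worsening, tolerated | No dose change; re-examine within 2 weeks | Interrupt or stop |
| Grade 1, acute or worsening, tolerated | No dose change, no intervention | Interrupt or stop |
| Any grade, symptoms unacceptable to the patient | Hold (footnote) | No conflict |
| Eye pain as an event in itself | No row of its own; hold allowed at discretion | Interrupt or stop |

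**2. Whether another rule requires the hold**

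- The discretion in Section 6 allows a hold for eye pain but does not require one.
- The footnote tests tolerability, not acuity or worsening.
- The other-toxicity row of Table 7 asks for prolonged, clinically significant toxicity of grade 2 or more, which an acute presentation need not be.
- The day 1 cycle criteria and the 21-day withdrawal rule in Section 6 both accept tolerable grade 2.
- The off-treatment criterion in Section 5.10 covers unacceptable adverse events, not a temporary hold pending examination.

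None makes the hold mandatory in the fourth and fifth situations.

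**3. Whether the table could carry such a rule**

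It already does for suspected interstitial pneumonitis: "Hold pending diagnosis", with no grade attached. It also has rows for the liver stop in the same safety text ("OSI-779 dosing should be interrupted or discontinued if total bilirubin is" >3 x ULN, or transaminases >5 x ULN).

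**4. Size**

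- Patients still on erlotinib: not given. Assumed range 0 to 5.
- Keratitis rate: under 3% (Section 7.1.1.1).
- Expected keratitis cases of any grade: 0.03 × 0 = 0, and 0.03 × 5 = 0.15 as the upper limit. The gap concerns only part of these.
- Continued dosing: no firm bound follows. Grade 1 has no duration limit, and for grade 2 the dose on day 14 is not governed by either row.
- Time since closure: 22 March 2016 to 22 March 2019 is 3 × 365 = 1,095 days; from there to the version date of 7 January 2020 is 291 days; together 1,386 days.

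**The case against.** The strongest objection is practical. Section 16.4 says that the treatment arms have been closed since 3/22/2016 and that the study is open for molecular profiling only. Table 7 may govern nobody. This stands, and it keeps the point minor. It does not dispose of it: Sections 3.3 and 5.3 describe the arms as no longer recruiting, treatment runs until progression, and no text says that the last erlotinib patient has stopped.

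A reader might infer that the protocol obliges sites to keep dosing a patient with eye pain. The documents do not support that. The MK-2206 adverse event list treats eye pain and keratitis as separate terms, so eye pain is an event that Table 7 does not cover, and the dose may be held for it even when keratitis is also present. Section 6 also calls its tables guidelines, and an examination within two weeks may be an early one. The shortfall is that the hold is optional.

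A reader might also infer that any new grade 1 keratitis should stop the drug. The safety text does not say so; its trigger is an acute or worsening disorder, with eye pain as the example. How often such a presentation would be graded 1 or 2 depends on CTCAE version 4, which the documents cite but do not reproduce.

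Nor does the liver comparison show that the eye instruction was singled out for omission. Table 7 also has no specific row for the gastrointestinal perforation, bullous skin or dehydration instructions in the same safety text; the perforation stop appears in Section 9.1.1.11. The table was not a full copy. Finally, Appendix A describes itself as background, so Section 6 prevails. That settles precedence, but it also means that an instruction found only in the appendix does not bind sites.

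**Conclusion.** The inconsistency is real and narrow. Section 6 permits but does not require an erlotinib hold for acute or worsening eye symptoms, mainly in symptomatic keratitis that is below grade 3, has not passed 14 days if grade 2, and is tolerated. Day 14 of grade 2 is in neither row.

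This is a minor safety-consistency point, worth considering. It matters only if a patient is still taking erlotinib. Fewer than 0.15 expected keratitis cases rests on the assumption of at most 5 such patients, and zero patients is possible.

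The conclusion also rests on reading the footnote's tolerability clause as applying to every row. If it applies only to rash and diarrhea, which its first clause names, the gap also takes in early keratitis that the patient does not tolerate. The documents support neither a claim that patients are now being harmed nor any claim about the trial's endpoints or analyses.

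**What to change.** Add to the Table 7 keratitis row: *hold for acute or worsening eye symptoms such as eye pain, regardless of grade, pending eye examination*. This follows the form of the table's pneumonitis rule. In the same row, change > 14 days to ≥ 14 days so that day 14 has an instruction.

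The cost is one line and one symbol in one table. The downside is a few missed doses in an affected patient while the eye is examined. If the sponsor confirms that no patient remains on erlotinib, the point is closed for this trial, and the wording should be corrected wherever Table 7 is reused.
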